Rationale	
Open questions are still needed to be answered:
 
 - In the exclusive radiotherapy scenario, does ENI produce an overall or biochemical relapse free survival advantage over prostate only radiotherapy for intermediate/high/very high-risk cases? - If ADT is added to prostate only radiotherapy, in intermediate/high/very high-risk cases, ENI is any longer needed?

	
 - Is ENI, associated or not to ADT, linked with an OS or bRFS survival advantage in patients submitted to adjuvant postsurgical prostate radiotherapy? - Additional toxicity due to the larger volumes treated might be reduced by more sophisticated radiotherapy techniques when ENI is added to prostate? - How many Radiation Oncology centers use ENI to treat patients with intermediate/high/very high-risk prostate cancer, with or without ADT? - The data obtained from the present observational study will be helpful for designing a subsequent randomized controlled trial.
End-points	
Primary:
 
 - Overall survival; 
Secondary:
 
 - Cause-specific (CSS) and Biochemical Relapse Free survival (bRFS); - acute and late toxicity evaluation (rectal, bladder, bowel toxicity, according to CTCAE v.4 scale); - Quality of Life deterioration (according to the UCLA-PCI scale).
Study design	
This is a prospective, multicenter, observational cohort study aimed to describe the advantage/disadvantage of different treatments of patients with intermediate/high/very high risk prostate cancer, through a web-based database.
 
The study will include all consecutive patients affected by intermediate, high or very high-risk prostate cancer that fit to the inclusion criteria and who are evaluated at each Centre involved in the study. Patients may have already undergone or not to radical prostatectomy and/or pelvic lymphadenectomy.
 
Phase 1: Establishment of the network of Centers involved in the study Phase 2: Activation and recruitment of eligible cases Phase 3: Follow-up (1,3,6,12/18,24/30/36 months)

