Statistical considerations	
Sample size
 
From previous experiences of the AIRO Prostate Cancer Study Group (AIRO PCSG), at least 15-20 Radiotherapy Centers from different regions of the country will be able to participate to the study. It is conceivable an accrual of at least 400-500 patients within 2 years and a further follow up of at least 3 years for each patient. For intermediate and high risk patients, an overall survival at 5 years of 0.8 has been previously reported (RTOG 94-13). According to the primary end-point of the study, a sample size of 400 patients will allow to estimate a 5-year survival of 0.8 with 95% confidence interval of 0.76-0.84.
 
Statistical Analyses
 
In order to describe the data, mean and standard deviation will be used for normally distributed continuous variables, median and ranges for non-normally distributed continuous variables, proportions and percentages for

	
categorical variables. Associations between two categorical variables will be assessed through the Pearson's chi-squared test or Fisher test, when appropriate. Differences between two-sample central tendencies will be assessed with a two independent sample t-test or Mann-Whitney U test or Wilcoxon, depending on distribution of the continuous variable.
 
Analysis of variance and covariance and regression models will be used for evaluating the associations of some variables with survival taking account of possible confounders.
 
In order to compare groups in terms of survival end-points, Kaplan-Meier curves will be estimated and log-rank tests will be performed.
 
Periodical analyses are planned in order to check the quality of entered data. The analyses will be performed by using STATA 13 (StataCorp. 2013. Stata Statistical Software: Release 13. College Station, TX: StataCorp LP) or SPSS Statistical Software.

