Inclusion/exclusion criteria	
Every prostate cancer patient consecutively evaluated at the recruiting Centers and planned to receive radical exclusive or post-operative radiotherapy will be registered; this registration includes demographic and staging results data.
 
Only intermediate, high, very high patients will have, however, treatment and follow up CRF compiled, based on the inclusion criteria
 
Inclusion criteria
 
Men older than or aged 18 years;
 
Histologically confirmed intermediate, high or very high risk prostate cancer patients (NCCN classification: Intermediate Risk T2b and T2c or Gleason Score 7 or PSA value between 10 and 20 ng/mL; High risk: T3a or Gleason score 8-10 or PSA > 20 ng/ml; Very high risk: T3b-T4 or patients with multiple adverse risk factors reported in the high risk category that may be shifted in the very high risk group
 
Patients eligible for -and actually submitted to radical radiotherapy treatment (+/- androgen deprivation) or adjuvant radiotherapy treatment after surgery (radical prostatectomy +/- pelvic lymphadenectomy);
 
No other synchronous or previous malignant tumor other than skin basal cell carcinoma;
 
Patients able to understand and sign the appropriate informed consent;
 
Patients able to fill the Quality of Life (QoL) questionnaire;
 
Exclusion criteria
 
Patients aged less than 18;
 
Patients not eligible for -and actually not submitted to- radical radiotherapy treatment (+/- androgen deprivation) or adjuvant radiotherapy treatment after surgery (radical prostatectomy +/- pelvic lymphadenectomy);
 
Low risk prostate cancer (<T2b and T2c or < Gleason Score 7 or PSA value < 10 ng/mL);
 
Patients with synchronous or previous malignancy other than skin basal cell carcinoma;
 
Patients able to understand and sign the appropriate informed consent (IC) who decide not to subscribe IC;
 
Patients not able to understand and sign the appropriate informed consent (IC)
 
Patients unable to fill the QoL questionnaire.

Study duration	Estimated total time of recruitment is 2 years. It will be followed by a 3 years period of follow up for each patient.

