Visits and exams	
Every prostate cancer patient consecutively evaluated at the recruiting Centers and planned to receive radical exclusive or post-operative radiotherapy will be registered; this registration includes demographic and staging results data.
 
Only intermediate, high, very high patients will have, however, treatment and follow up CRF compiled, based on the inclusion criteria
 
Eligible patients will then receive all the information necessary to formulate their adhesion to the study and finally the physician will fill in the “Pretreatment” CRF that will include: Demographic Information; Anamnestic data; Initial diagnosis (date; PSA at diagnosis); Risk factors; Staging; Quality of life and symptoms caused by prostate cancer; General quality of life;
 
The choice of the treatment will be done based on commonly used international guidelines and on the specific internal protocol of each participating Center.
 
Since this study is observational, involved patients will be treated following good clinical practice and institutional policies procedures.
 
Clinical outcomes and variables, demographic features, dosimetric analysis and acute/late toxicities of both RT (with and without ENI) and ADT will be reported.

	
Follow-up visits on 1,3,6,12/18,24/30 and 36 months
 
Every patient will be contacted by the physicians to fill a CRF that will include: Vital state (mortality, date and causes of death) or loss to follow up; Last PSA value; Other treatments (drugs); type of RT and ADT treatment Acute and late toxicities; Biochemical Relapse with PSA value and date of last PSA; Quality of life and symptoms due to prostate cancer; General quality of life.
 
Survival status (mortality, date and cause of death) or exit from the study; If macroscopical recurrence or disease progression will occur, the radiological exams (if performed) will be reported; Further treatments received/planned after radiotherapy; The last available PSA;
 
Acute/Late toxicity
 
Genitourinary and gastrointestinal toxicity due to radiation therapy.
 
A CRF will be completed regarding: Technical characteristics of the radiation treatment; Quality of life and complications due to prostate cancer; General quality of life

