Centers involved will identify all the eligible cases with biopsy proven prostate adenocarcinoma. Patients who are candidate to get involved in the study will be contacted by the physician in charge of the study for each Center. **Every** prostate cancer patient consecutively evaluated at the recruiting Centers and planned to receive radical exclusive or post-operative radiotherapy will be registered; this registration includes demographic and staging results data; only intermediate, high, very high patients will have, however, treatment and follow up CRF compiled (both treated with or without ENI; +/- ADT).

Eligible patients will then receive all the information necessary to formulate their adhesion to the study and finally the physician will fill in the “Pretreatment” Case Report Form (CRF) that will include:

- Demographic Information (date of birth, study title, civil state, working information);
- Another person (relatives, friends,...) as a contact to minimize follow up loss;
- Anamnestic data (height, weight, smoking habit, comorbidities, Cumulative Illness Rating Scale [44], Attachment 1);
- Initial diagnosis (date; PSA at diagnosis);
- Risk factors;
- Staging (clinical TNM, date of biopsy, Gleason score, total number of samples, number of positive samples);
- Quality of life and symptoms caused by prostate cancer (using Italian UCLA Prostate Cancer Index) [45, 46];
- General quality of life (SF-12 Standard V1) [47].

The choice of the treatment will be done based on commonly used international guidelines and on the specific internal protocol of each participating Center.

Since this study is observational, involved patients will be treated following *good clinical practice* and institutional policies procedures.

Clinical outcomes, (such as overall survival and biochemical relapse free survival) and variables, demographic features, dosimetric analysis and acute/late toxicities of both RT and ADT will be reported.

Phase 3: Follow-up (1, 3, 6, 12, 18, 24, 30, 36 months)

After the end of the radiotherapy treatment patients will be evaluated 1, 3, 6, 12, 18, 24, 30 and 36 months since the last session.

Every patient will be contacted by the physicians to fill a CRF that will include:

- Vital state (mortality, date and causes of death) or loss to follow up;
- Last PSA value;

- Other treatments (drugs);

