- Treatment : type of treatment, start date, PSA value before treatment; if surgery type of surgery and pathological TNM, margins, Gleason Score, number of positive lymph nodes; if external RT (intent, modality, technique, dose/fraction, volumes, concomitant hormonal therapies); if brachytherapy (type, intent, dose); if hormone therapy (type of drugs, start and end date, total duration);
- Acute and late toxicities;
- Biochemical Relapse with PSA value and date of last PSA;
- Quality of life and symptoms due to prostate cancer (Italian UCLA-PCI);
- General quality of life SF-12.

Toxicity and response evaluation

The enrolled patients will undergo the first follow up visit one month after the end of radiotherapy. On that occasion, clinical examination will be performed and previously prescribed blood tests, if required, will be evaluated. Genitourinary and gastrointestinal toxicity due to radiation therapy for prostate cancer will be reported according to the NCI Common Terminology Criteria for Adverse Events (CTCAE) version 4 for adverse event (AE) reporting. The CTCAE version 4 is identified and located on the CTEP web site at:

http://ctep.cancer.gov/protocolDevelopment/electronic_applications/ctc.htm [48]

In addition, a Case Report Form (CRF) will be completed (see Attachment 2), regarding:

- Technical characteristics of the radiation treatment (dose, volume, technique, association or not with hormonal therapy);
- Quality of life and complications due to prostate cancer (according to Italian UCLA-PCI) [45, 46];
- General quality of life (SF-12 Standard V1) [47].

Thereafter patients will be evaluated at 3-months, 6-months and 12-months after the end of radiotherapy, and then every 6 months for at least 24 months. During all those scheduled follow up visits, PSA level (jointly with testosterone, in case of association with hormonal therapy) and

previously prescribed blood texts if required, will be evaluated. Patients will undergo clinical examination, and genitourinary and gastrointestinal toxicity will be assessed according to the CTCAE v4.0 classification scale). In addition, a CRF (see Attachment 3) will be completed at each visit, regarding:

- Survival status (mortality, date and cause of death) or exit from the study;
- If macroscopical recurrence or disease progression occurred, the radiological exams (if performed);
- Further treatments received/planned after radiotherapy;
- The last available PSA;

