- Quality of life and complications due to prostate cancer (Italian UCLA-PCI) [45, 46];
- General quality of life (SF-12 Standard V1) [47].

The Italian UCLA-PCI and SF-12 Standard V1 questionnaires reported in Attachment 2 and Attachment 3 [45, 46, 47] will be given by the referring physician and self-compiled by patients in physician's absence, eventually with the help of a nurse if necessary; thereafter, the referring physician will insert the data to the database.

Data Collection, Confidentiality

Data will be collected through an *ad hoc* web based software, built to guarantee:

1. Respect of the Italian laws and of the international rules about GMP and privacy, according also to the general principles fixed by the Helsinki declaration and its subsequent updates;
2. The anonymization of the patient records;
3. The possibility for each participating Center to have unrestricted access to its own data;
4. The restriction of the access to the full dataset composed by the sum of the records provided by the single Centers; this will be allowed only after the authorization of the PI and the Study Coordinator. Once the study will be completed, access to the whole database will be possible only after having obtained the authorization of the AIRO President in charge and of the AIRO Board;
5. The safe storage of the data, along with that of the previous AIRO-PCSG studies, along with.

The use of the software will be elucidated to the single participating Centers in *ad hoc* start up

meetings, to guarantee an appropriate and homogeneous data collection; a tool bar will however be devised, to automatically verify inconsistencies in the data collected.

Statistical Considerations

Sample size

From previous experiences of the AIRO PCSG [49, 50], at least 15-20 Radiotherapy Centers from different regions of the country will be able to participate to the study. It is conceivable an accrual of at least 400-500 patients within 2 years and a further follow up of at least 3 years for each patient. For intermediate and high risk patients, an overall survival at 5 years of 0.8 has been previously reported (RTOG 94-13) [51]. According to the primary end-point of the study, a sample size of 400 patients will allow to estimate a 5-year survival of 0.8 with 95% confidence interval of 0.76-0.84 [52].

Statistical Analyses

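### The only precision figure for overall survival is set at 5 years, but the described follow-up ends at 3 years per patient

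*Combined protocol and SAP*

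**What the plan says.** OS is the primary endpoint in the synopsis (End-points) and in the summary that closes Aims of the study. Neither place gives a time point or a time origin.

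The precision statement is in Statistical Considerations, Sample size, and is repeated in the synopsis: "a sample size of 400 patients will allow to estimate a 5-year survival of 0.8 with 95% confidence interval of 0.76-0.84". It is presented as following from the primary endpoint. The same paragraph expects "an accrual of at least 400-500 patients within 2 years" and "a further follow up of at least 3 years for each patient".

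Follow-up is described as follows:

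- Synopsis, Study duration, after two years of recruitment: "It will be followed by a 3 years period of follow up for each patient". Study Duration and Accrual and timeline in the body also give three years, without the words that make it a minimum.
- Phase 3: Follow-up: "patients will be evaluated 1, 3, 6, 12, 18, 24, 30 and 36 months since the last session".
- Synopsis, Visits and exams: "Follow-up visits on 1,3,6,12/18,24/30 and 36 months". The synopsis Study design row ends at the same month.
- Toxicity and response evaluation, after the month-12 visit: "and then every 6 months for at least 24 months". This is a floor that also lands on month 36.
- Attachment 3, the follow-up form: its title ends at month 36, although its list has a month 9 and lacks month 30, unlike Phase 3.

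Vital status is recorded on these visit forms. Statistical Analyses names Kaplan-Meier curves and log-rank tests, with no landmark time and no data cut-off.

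**The concern.** The horizon of the precision statement and the horizon of data collection differ by two years. The figure is the only rationale given for the number of patients. A reader would take it as a promise of a 5-year OS known to within 0.04, yet the documents describe no data collection that would deliver it. The protocol also says the data will help design a randomised trial, so a 5-year figure could be carried into later planning.

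The consequence is limited. No powered test depends on this interval, and OS up to month 36 can be estimated with better precision than 0.04.

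**Working it through.** **Inputs from the documents.** n = 400 (planned accrual 400 to 500), 5-year OS 0.80, two-sided 95%, accrual over 2 years, last visit at month 36 after the last radiotherapy session.

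**Step 1: reproduce the stated interval.** Simple binomial interval:

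0.80 ± 1.96 × √(0.80 × 0.20 / 400) = 0.80 ± 0.0392, or 0.761 to 0.839.

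This rounds to the plan's 0.76 to 0.84. The formula takes 5-year status as known for everyone counted. There is little room for loss: a half-width of 0.04 needs 1.96² × 0.16 / 0.04² ≈ 384.1, so 385 patients with known 5-year status.

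**Step 2: follow-up as scheduled.** With the clock at the end of radiotherapy, each patient's observation stops at month 36, so 0 of 400 are at risk at month 60. Kaplan-Meier then gives no 5-year estimate for any n. With an earlier origin, such as diagnosis, only patients whose radiotherapy ended at least 60 − 36 = 24 months after that origin could reach month 60.

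**Step 3: reading three years as a minimum.** The documents give no closing date, so I assumed one common close, uniform accrual over 2 years, constant hazard, no losses, and the clock at study entry.

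- Hazard: λ = −ln(0.80)/5 = 0.0446 per year, S(t) = exp(−λt).
- Close A years after last entry: the proportion still under observation is G(u) = 1 for u ≤ A and (A + 2 − u)/2 after that.
- Half-width at t (large-sample Greenwood): 1.96 × S(t) × √(I/n), with I = ∫₀ᵗ λ / [S(u)G(u)] du.
- Number at risk at t: n × S(t) × G(t).

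For A = 3 and t = 4.9, S = 0.804 and I = 0.468, so the half-width is 1.96 × 0.804 × √(0.468/400) = 0.054.

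| Close after last entry | Time | n = 400: half-width (at risk) | n = 500: half-width (at risk) |
|---|---|---|---|
| 3 years | 4.9 years | 0.054 (16) | 0.048 (20) |
| 3 years | 5 years | none (0) | none (0) |
| 3.25 years | 5 years | 0.0485 (40) | 0.043 (50) |
| 3.5 years | 5 years | 0.044 (80) | 0.040 (100) |
| 4 years | 5 years | 0.041 (160) | 0.037 (200) |

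Simulation (6,000 runs per case) of the Kaplan-Meier estimate at 5 years gave 0.047, 0.044 and 0.041 for n = 400, and 0.043, 0.040 and 0.037 for n = 500, with 94 to 95% coverage of the nominal 95% interval. Closes at 3.25 and 3.5 years would let the last patient complete month 36 if entry to the end of radiotherapy takes 3 or 6 months. That interval is also an assumption.

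**Step 4: what the schedule supports.** Under the same constant hazard, S(3) = exp(−3 × 0.0446) = 0.875.

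- n = 400: 0.8747 ± 1.96 × √(0.8747 × 0.1253 / 400) = 0.8747 ± 0.0324, or 0.842 to 0.907. Expected deaths: 400 × 0.1253 ≈ 50, against 400 × 0.20 = 80 by 5 years.
- n = 500: half-width 0.029.
- If 10 to 20% of the 400 lack 3-year status (assumed range), the complete-case half-width is 0.034 (n = 360) to 0.036 (n = 320).

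**The case against.** The best defence is that the sample-size paragraph itself makes three years a minimum, and the toxicity section uses similar wording. Two years of accrual plus at least three of follow-up makes a study of about five years, which may be where the 5-year horizon came from. Kaplan-Meier is built for such staggered follow-up. Because visits count from the end of radiotherapy, a common close would fall later than three years after last entry. With 500 patients and a close at 3.5 years, the stated 0.04 is met; with 400 the half-width is 0.044, about 0.005 wider than 0.039.

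Much of this stands. The statement that nobody reaches 5 years belongs to one reading of the follow-up and to a clock starting at the end of radiotherapy, and the size of any shortfall on the other reading rests on my assumptions. But the floor wording permits longer follow-up without describing any contact, linkage or cut-off that would produce it, and three other sections give three years flat. A study lasting five calendar years does not give patients five years each: with a close three years after last entry, only the very first entrants approach year 5.

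An origin at diagnosis does not rescue the interval either. It would bring delayed entry, which the simple binomial formula ignores.

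It is also fair that a 3-year OS of 0.875 appears nowhere in the documents and depends on a constant hazard, and that the choice of landmark belongs to the sponsor.

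**Conclusion.** The concern holds. The interval is computed correctly but at a time point that the described follow-up does not reach. As scheduled, with the clock at the end of radiotherapy, 0 of 400 patients are followed to 5 years and 5-year OS cannot be estimated. If three years is a minimum, the precision runs from no 5-year estimate at all (close at 3 years) to the stated 0.04 or better (500 patients, close at 3.5 years or later), depending on a date the plan does not give. Those figures rest on uniform accrual, constant hazard, no losses and a clock from entry.

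Confidence is high that the 5-year figure is unsupported as written, but does not extend to any particular size of shortfall. This should be fixed. It does not call the sample size into question.

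**What to change.** In the sample-size text and its synopsis copy, restate the precision at a time the schedule supports. For example:

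> Assuming a constant hazard consistent with a 5-year OS of 0.80, and vital status known at 3 years, 400 patients give a 3-year OS of about 0.875 with a 95% CI of about 0.84 to 0.91.

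Then:

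- define the OS time origin;
- say whether month 36 is the minimum or the end of follow-up, and use one wording and one visit list throughout the synopsis, the duration and follow-up sections, and Attachment 3;
- label any remaining 5-year figure as an extrapolation.

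This costs text changes and a choice of landmark by the sponsor, with no extra patients or visits. The drawbacks are fewer deaths at the landmark (about 50 rather than 80), the constant-hazard assumption behind 0.875, and no direct match to the 5-year benchmark cited for planning.

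If the sponsor prefers to keep the 5-year figure, the protocol should describe vital-status collection to month 60 and state the data cut-off. That costs more: up to two further years of vital-status contact per patient.

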In summary, the study aims at the definition of survival, toxicity and QoL data in a representative sample of intermediate, high and very high risk prostate cancer patients consecutively recruited in Italian Radiation Oncology Centres over two years. Parameters considered will be OS, CSS and bRFS, toxicity (rectal, bladder, bowel toxicity, according to CTCAE v.4 scale) and QoL (according to the SF-12 scale and UCLA-PCI scale). Primary end point will be OS. Secondary endpoints will be CSS, bRFS, gastrointestinal and genitourinary toxicity, QoL deterioration.

Study Design

This is a prospective, multicenter, observational cohort study aimed to describe the advantage/disadvantage of different treatments of patients with intermediate/high/very high risk prostate cancer, through a web-based database.

Study Duration

The recruitment period, taking into account the needed sample size (*v.infra*) will be of two years, followed by three-year follow up period for each patient, with an accrual of at least 400-500 patients.

Population, Procedures

The study will include all consecutive patients affected by intermediate, high or very high-risk prostate cancer that fit the inclusion criteria and who are evaluated at each Centre involved in the study. Patients may have already undergone or not to radical prostatectomy and/or pelvic lymphadenectomy.

Inclusion criteria

- Men older than or aged 18 years;
- Histologically confirmed intermediate, high or very high risk prostate cancer patients (NCCN classification: Intermediate Risk T2b and T2c or Gleason Score 7 or PSA value between 10 and 20 ng/mL; High risk: T3a or Gleason score 8-10 or PSA > 20 ng/ml; Very high risk: T3b-T4 or patients with multiple adverse risk factors reported in the high risk category that may be shifted in the very high risk group
- Patients eligible for -and actually submitted to- radical radiotherapy treatment (+/- androgen deprivation) or adjuvant radiotherapy treatment after surgery (radical prostatectomy +/- pelvic lymphadenectomy);
- No other synchronous or previous malignant tumor other than skin basal cell carcinoma;
- Patients able to understand and sign the appropriate informed consent;
- Patients able to fill the QoL questionnaire;

Exclusion criteria

- Patients aged less than 18;

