In order to describe the data, mean and standard deviation will be used for normally distributed continuous variables, median and ranges for non-normally distributed continuous variables, proportions and percentages for categorical variables. Associations between two categorical variables will be assessed through the Pearson's chi-squared test or Fisher test, when appropriate. Differences between two-sample central tendencies will be assessed with a two independent sample t-test or Mann-Whitney U test or Wilcoxon, depending on distribution of the continuous variable.

Analysis of variance and covariance and regression models will be used for evaluating the associations of some variables with survival taking account of possible confounders.

In order to compare groups in terms of survival end-points, Kaplan-Meier curves will be estimated and log-rank tests will be performed.

Periodical analyses are planned in order to check the quality of entered data.

The analyses will be performed by using STATA 13 (StataCorp. 2013. Stata Statistical Software: Release 13. College Station, TX: StataCorp LP) or SPSS Statistical Software.

Ethical committee

After the final approval by the AIRO-PCSG, the Protocol will be submitted to the Ethical Committee (EC) of the Study Coordinating Centre; when it will be approved, the single participating Centres will consequently apply for approval of their EC. According to the judgment of the PI and of the Study Coordinator, the first patient will be enrolled when a sufficient number of Centres will have obtained EC approval. This will be the starting date for the study.

The present study will be performed in accordance with the present protocol, with the principles of Good Clinical Practice in the respect of the ICH GCP guidelines and the ethical principles contained in the Helsinki declaration.

Publication rules

Interim and final results of the study will be published under the final responsibility of the PI and of the Study Coordinator.

The following publication rules will be enforced:

1. The participating Centers should approve the paper;
2. Only Centers contributing to more than 5% of the cases collected will have a person quoted as Author of the paper; however, every Center contributing to the common database, as well as the people working to realize the Study, will be publicly quoted and their contribution acknowledged in the paper;
3. Authorship is granted in proportion to:
 - a. the cases contributed to the database;

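### QoL deterioration is measured repeatedly on the same men, but the plan does not define it as a change from baseline and assigns it no paired or repeated-measures analysis

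*Combined protocol and SAP*

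**What the plan says.** **Endpoint.** The synopsis lists, among the secondary end-points, "Quality of Life deterioration (according to the UCLA-PCI scale"). The summary closing Aims of the study says: "Secondary endpoints will be CSS, bRFS, gastrointestinal and genitourinary toxicity, QoL deterioration"; there the QoL instruments are SF-12 as well as UCLA-PCI. Neither place gives a domain, visit, threshold or formula for deterioration.

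**Measurement.** The Pretreatment CRF (Phase 2) includes "Quality of life and symptoms caused by prostate cancer (using Italian UCLA Prostate Cancer Index") and SF-12. Both questionnaires recur in the follow-up CRFs. Phase 3 sets the schedule: "After the end of the radiotherapy treatment patients will be evaluated 1, 3, 6, 12, 18, 24, 30 and 36 months since the last session".

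**Analysis.** The synopsis and the Statistical Analyses section carry the same text:
- Continuous variables: "Differences between two-sample central tendencies will be assessed with a two independent sample t-test or Mann-Whitney U test or Wilcoxon", with the choice resting on the distribution of the variable.
- Categorical variables: "Associations between two categorical variables will be assessed through the Pearson's chi-squared test or Fisher test, when appropriate".
- Models: analysis of variance and covariance are named, and "regression models will be used for evaluating the associations of some variables with survival taking account of possible confounders".

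No paired t-test, McNemar test or repeated-measures model is named, and no test is assigned to QoL.

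**The concern.** Deterioration needs a reference point, and the only QoL reference the study collects is each man's own score before treatment. Aim 5 brings in historical data, but for clinical outcomes and toxicities, not for QoL. Change from baseline is therefore the natural reading, although it is inferred from the visit schedule and not stated.

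The t-test and categorical tests named assume that observations are independent. Two scores from one man are not, and neither are his scores at successive visits. The stated rule for choosing a test is the shape of the distribution, so nothing in the text tells an analyst to pair the data. Treating baseline and follow-up scores as two unrelated samples discards the within-patient correlation. If that correlation is positive, the standard error of the change is overstated and a real worsening may be reported as not significant. The study is meant to describe advantages and disadvantages of different treatments and to inform a randomized trial, so the loss would matter most in the ENI, ADT and treatment-setting subgroups, which are smaller than the full cohort.

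**Working it through.** **The plan's own figure.** The only stated design figure concerns survival: "a sample size of 400 patients will allow to estimate a 5-year survival of 0.8 with 95% confidence interval of 0.76-0.84". The Wald interval is 0.8 ± 1.96 × √(0.8 × 0.2 / 400) = 0.8 ± 0.039, that is 0.761 to 0.839. It reproduces. There is no corresponding figure for QoL.

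**Inputs for the QoL check.** From the documents: N = 400, with baseline and follow-up scores on the same men. Assumed, because the documents give none of these: equal SDs (scores in SD units), within-patient correlation ρ = 0.5 with range 0.3 to 0.7, changes of 0.2 and 0.3 SD, and subgroups of 100 and 200.

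**Standard error of the mean change in N men.**
- Independent-sample formula: √(2/N)
- Paired formula: √(2(1 − ρ)/N)
- Ratio: 1/√(1 − ρ)

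At N = 400 the independent-sample 95% half-width is 1.96 × √(2/400) = 0.139 SD. The actual two-sided error rate of that test on paired data, nominally 5%, is 2[1 − Φ(1.96/√(1 − ρ))].

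| ρ | Paired half-width, N = 400 (SD) | Width ratio | Actual type I error |
|---|---|---|---|
| 0.3 | 0.116 | 1.20 | 1.9% |
| 0.5 | 0.098 | 1.41 | 0.56% |
| 0.7 | 0.076 | 1.83 | 0.035% |

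A simulation at N = 400 and ρ = 0.5 gave 0.6%. At ρ = 0 nothing is lost. At a negative ρ the error reverses: at −0.2 the interval is 0.91 times the correct width.

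**Power on the same pairs.** With SE_p the paired standard error and SE_i the independent one, paired power is Φ(d/SE_p − 1.96). The independent test rejects with probability Φ((d − 1.96 × SE_i)/SE_p). Worked case, n = 200, ρ = 0.5, d = 0.2: SE_i = 0.100 and SE_p = 0.0707. Paired: Φ(2.83 − 1.96) = Φ(0.87) = 81%. Independent: Φ((0.2 − 0.196)/0.0707) = Φ(0.06) = 52% (53% by simulation).

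| n (ρ = 0.5) | 0.2 SD, independent / paired | 0.3 SD, independent / paired |
|---|---|---|
| 400 | 89% / 98% | 99.9% / 100% |
| 200 | 52% / 81% | 93% / 99% |
| 100 | 22% / 52% | 59% / 85% |

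At n = 200 and 0.2 SD the pair is 52% / 67% at ρ = 0.3 and 53% / 95% at ρ = 0.7.

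**Binary item.** For a problem whose frequency goes from 20% to 27% (assumed, with within-patient phi 0.5), simulated power is 33% with chi-squared against 58% with exact McNemar at n = 200, and about 70% against 89% at n = 400.

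**Use between different patients.** The independent t-test applied to change scores in two groups of 200 gave a simulated type I error of 5.3%, consistent with 5%. The problem lies in the pairing of observations, not in the test itself.

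**The case against.** A reader might infer that the plan's QoL intervals are too wide, full stop, because the wrong test has been chosen. The documents do not support that.

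- **No test is assigned to QoL.** The quoted sentence is a general list of methods. No baseline-versus-follow-up comparison and no QoL interval is promised. The loss arises only if an analyst applies the independent-sample tests to the same men's scores. This stands.
- **Comparisons between different patients are legitimate.** Independent-sample tests are valid for change scores between groups, for scores at one visit between groups, and, with chi-squared or Fisher, for the proportion of men who deteriorated. This stands. But the plan defines neither a change score nor a per-patient category. Visit scores compared without baseline ignore information already collected, and none of these tests handles several correlated visits together.
- **Wilcoxon is listed apart from Mann-Whitney and may mean signed-rank.** That is plausible, particularly since the UCLA-PCI items are ordinal. The text does not settle it. If signed-rank is meant, approximately normal scores would still go to the independent t-test, and paired categorical items would have no suitable test.
- **The loss is modest in the full cohort.** At N = 400 even a 0.2 SD change keeps 89% power, and at 0.3 SD the loss is slight except near n = 100. This stands.
- **A pre/post change does not isolate the effect of radiotherapy.** Some men enter after prostatectomy or may have had neoadjuvant hormones. So it would also be too much to say that the plan understates harm from treatment. What can be missed is a change in QoL, whatever its cause.

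**Conclusion.** The point holds in conditional form. The plan collects a baseline and repeated QoL scores but neither defines deterioration nor names an analysis that clearly uses that structure. If the independent-sample tests are applied to baseline versus follow-up scores with positive correlation, the conclusion errs towards finding no change. The size rests on assumed correlations, SDs, effects and subgroup sizes and cannot be fixed from the documents. It ranges from slight in the full cohort at 0.3 SD to roughly 30 percentage points of power in subgroups of 100 to 200 at 0.2 SD and correlation 0.5. This is a worthwhile, inexpensive improvement to a secondary endpoint. Overall survival and N = 400 do not depend on it.

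**What to change.** In the synopsis (Statistical considerations) and in Statistical Analyses, add text to this effect:

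- QoL deterioration is the within-patient change from the pre-treatment UCLA-PCI or SF-12 score, by domain and visit. The synopsis ties the endpoint to UCLA-PCI alone, so state whether SF-12 belongs to it.
- Change within a group is tested with the paired t-test or the Wilcoxon signed-rank test, and with McNemar for binary items.
- Treatment groups are compared across visits with a linear mixed model for repeated measures: baseline score as covariate, visit as a categorical factor, treatment group, group-by-visit interaction, and correlation within patient.
- The independent-sample t-test, Mann-Whitney, chi-squared and Fisher tests are reserved for comparisons between different patients.

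The model needs one agreed list of visits. Phase 3 has month 30 and no month 9, whereas the heading of Attachment 3 has month 9 and no month 30; these should be reconciled.

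The cost is a few sentences and slightly more programming. No new data, visits or patients are needed, and STATA 13 and SPSS both fit these models.
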